## 6.0 PRETREATMENT EVALUATION (SEE APPENDIX A)

- 6.1 A complete history and physical to include performance status, recent weight loss, current weight and concurrent non-malignant disease and therapy. Detailed information on existing malignant lesions and sizes is required, within 2 weeks before starting therapy.
- 6.2 Laboratory studies shall include a CBC, platelet count, differential, urinalysis, chest x-ray, creatinine, electrolyte, bilirubin, SGOT, alkaline phosphate, and peripheral blood lymphocyte surface markers, LDH, assay for soluble CD20 if possible, and B2 microglobulin levels, to be done within 2 weeks before starting therapy.
- 6.3 Appropriate studies should be obtained to define fully the extent of disease. Bilateral bone marrow biopsy, chest x-ray and CAT scan of the area(s) of involvement should be performed within 2 months before therapy (within 1 month preferably, especially if there is any clinical evidence of rapidly changing adenopathy). Lymphangiogram is recommended but is optional. The measurements of masses detected by CT scan ideally should be recorded as the volume in cubic centimeters, or as the perpendicular diameters. All other masses should be recorded as the perpendicular diameter.
- 6.4 Baseline blood and bone marrow aspirates will be obtained for bcl-2 PCR. Contact our research nurse to make these arrangements, at the same time that eligibility screening is done. Please make these contacts early, so that candidate patients can have these studies done in a timely and efficient manner.
- 6.5 Immunophenotyping and gene rearrangement studies (PCR studies for bcl-2 mbr and mcr; and JH for bcl-2 negative patients) also should be performed on lymph node tissue, whenever possible. For fresh tissue obtained here, please arrange, through our research nurse, to have the sample triaged appropriately.

For biopsies done outside, prior to referral here, please arrange, through our research nurse, to have this archival tissue analyzed by [name].

For cases whose diagnosis is based on limited tissue sample (e.g., FNA), it is strongly encouraged to obtain more tissue. Please discuss such cases with the P.I., if it is felt that treatment plans need to proceed despite suboptimal diagnostic material.

If fresh tissue is obtained, please also perform nucleic acid flow cytometry, if possible.

- 6.6 Required tests include ejection fraction by echocardiography or MUGA to be performed as baseline. Smokers as well as those with any significant history of pulmonary disease should also have pulmonary function testing. These should be done within 3 months before starting therapy.
- 6.7 Location, type and size of all measurable or evaluable lesions must be recorded prior to treatment.

## 7.0 EVALUATION DURING STUDY (SEE APPENDIX A)

- 7.1. Patients shall be followed at least weekly with CBC, platelet count and differential and will be seen in our clinic after the second and fourth courses.
- 7.2 PCR in the peripheral blood will be followed every 6 months during the first 3 years, then every 12 months. PCR in the bone marrow will be followed every 6 months during the first 3 years, and every 12 months subsequently. For patients who are positive at the 6 month time point an additional PCR assay at 9 months is requested. For such patients who are still positive at 9 months, but who are subsequently negative at 12 months, yet another additional assay at 15 months is requested.
- 7.3 An SMA-12 shall be performed at least every other course or as frequently as needed to define drug toxicity.
- 7.4 Peripheral blood lymphocyte surface markers and Ig's every 3 months during therapy, and at least every 6-12 months off therapy until any abnormalities resolve.
- 7.5. Appropriate restaging every 3 courses, to include at least CXR, CT abdomen and pelvis, and BM Bx, and other tests to assess baseline measurable and assessable disease sites.
- 7.6 Cardiac re-evaluation as clinically indicated.
- 7.7 Off therapy monitoring should include restaging assessments (as outlined in section 7.5) at least every 6 months until relapse, or through year 5, and at least yearly thereafter.

## 8.0 CRITERIA FOR RESPONSE AND TOXICITY

### 8.1 Tumor Measurements

- a. Lesions will be measured bidimensionally in centimeters prior to each course of therapy. Masses detected by CT may be measured volumetrically in cubic centimeters.

- b. The longest diameter and its perpendicular will be measured on bidimensionally measured lesions. Size will be reported as the product of the diameters.
- c. Measurements should be made by the radiologist and/or clinician and recorded by the oncology research nurse under his/her supervision.
- d. An estimate of overall objective and subjective response will be made and recorded at each visit.

## 8.2 Response Definitions:

- I. A molecular complete remission is defined as a patient with an initially positive peripheral blood PCR who converts to negative on at least 2 consecutive occasions no less than 2 months apart. If, during the interval when 2 consecutive blood PCR's are negative, a marrow PCR is positive, such patients would not be considered a molecular complete responder. (Such cases of discordance are infrequent but can occur).
- II. Clinical CR: defined as those who achieve a normal state which includes no detectable evidence of disease on x-rays.
- III. Clinical CRu: defined as "CR unconfirmed" on the basis of minimal residual abnormalities on x-ray such as a residual mass <25% of original measurement (either by volume calculation or by the product of 2 diameters -- See Sect. 8.1) with no palpable disease on physical examination.
- IV. Clinical PR: a) 50-75% reduction in the product of palpable tumor diameters of in the tumor volume measurements by radiologic criteria (See Sect. 8.1) or any palpable disease such as peripheral node(s) > 1 cm in diameter or palpable abdominal mass with histological evidence of lymphoma cells.
- V. Clinical minor response or failure includes, <50% tumor shrinkage or > 50%, but with tumor regrowth between courses.

- 8.3 All toxicities encountered during the study will be evaluated according to the grading system (0-4) in Appendix D and recorded prior to each course of therapy. Duration and treatment will be recorded. Life-threatening toxicities should be reported immediately to the Study Chairman.

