## 9.0 CRITERIA FOR REMOVAL FROM THE STUDY

- 9.1 Minor responses or failures to respond after delivering the first 4 courses of treatment in this protocol will be removed from the study.
- 9.2 Patients who relapse after achieving remission will be considered for ABMT or if not eligible will be treated with the salvage protocol of highest priority.

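### The same clinical response percentages apply to tumour volume and to the product of two diameters, so a CT mass can change response category with the measurement method

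*Combined protocol and SAP*

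**What the plan says.** The response categories are in section 8.2:

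- **CRu (part III):** minimal residual abnormality, for example a "residual mass <25% of original measurement (either by volume calculation or by the product of 2 diameters", and nothing palpable on examination.
- **PR (part IV):** "50-75% reduction in the product of palpable tumor diameters of in the tumor volume measurements by radiologic criteria", or palpable disease with histological evidence of lymphoma.
- **Minor response or failure (part V):** "Clinical minor response or failure includes, <50% tumor shrinkage or > 50%, but with tumor regrowth between courses". No measure is named.

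The measurement rules are in two places. At baseline, section 6.3 says "The measurements of masses detected by CT scan ideally should be recorded as the volume in cubic centimeters, or as the perpendicular diameters". During the study, section 8.1a requires bidimensional measurement before each course but adds that "Masses detected by CT may be measured volumetrically in cubic centimeters". For lesions measured in two dimensions, 8.1b says "Size will be reported as the product of the diameters".

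The categories are used in three places. Section 10.4a compares CR (including CRu) and CR+PR between the arms, and 10.4b sets molecular response against those rates. Section 9.1 says "Minor responses or failures to respond after delivering the first 4 courses of treatment in this protocol will be removed from the study". Section 5.7.2 names CR, PR and CRu patients as the maintenance group.

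**The concern.** A product of two diameters is an area and a volume is cubic, so the same percentage means different amounts of shrinkage on the two scales. A mass that shrinks evenly always loses a larger percentage of its volume than of its diameter product. With identical percentages on both scales, volume is the easier route to PR and to the CRu range.

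The documents give no conversion, no rule for which measure governs when the two disagree, and no requirement that lesions, patients or arms be scored the same way. The secondary response rates could then mix two definitions in unknown proportions. The category also decides who is removed under 9.1 and who falls in the 5.7.2 group, so the ambiguity is not confined to tables.

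**Working it through.** The plan states no figure that depends on these cut-offs, so there is none to reproduce. The check is geometric.

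**Inputs.** The cut-offs are a 50% reduction (PR versus failure, 8.2 IV-V) and a 75% reduction, i.e. residual below 25% (CRu range versus PR, 8.2 III-IV). The allowed measures come from 6.3, 8.1 and 8.2. Proportional shrinkage is my assumption: every diameter is multiplied by the same factor s.

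**Formulas.** Product reduction = 1 − s². Volume reduction = 1 − s³.

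**Equivalent shrinkage at each cut-off.**

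| Cut-off met | s | Diameter reduction | Reduction on the other scale |
|---|---|---|---|
| 50% by product | √0.5 = 0.707 | 29.3% | 64.6% by volume |
| 50% by volume | ∛0.5 = 0.794 | 20.6% | 37.0% by product |
| 75% by product | √0.25 = 0.500 | 50.0% | 87.5% by volume |
| 75% by volume | ∛0.25 = 0.630 | 37.0% | 60.3% by product |

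There are two windows of disagreement. A diameter reduction from 20.6% to just under 29.3% is failure by product and PR by volume. One above 37.0% and up to 50% is PR by product and in the CRu range by volume.

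**Worked cases, starting from a 6 cm mass.**

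- To 4.5 cm: s = 0.75. Product: 1 − 0.5625 = 43.8%, failure. Volume: 1 − 0.4219 = 57.8%, PR.
- To 3.5 cm: s = 0.583. Product: 1 − 0.340 = 66.0%, PR. Volume: 1 − 0.198 = 80.2%, CRu range, provided nothing is palpable.

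**If shrinkage is not proportional.** Hold both in-plane diameters at a 25% reduction (product reduction 43.8%) and multiply the third axis by t. Volume reduction = 1 − 0.5625t.

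| Third axis | Volume reduction | Category by volume |
|---|---|---|
| unchanged (t = 1) | 43.8% | failure, agrees with product |
| down 10% (t = 0.90) | 49.4% | failure, agrees |
| down 15% (t = 0.85) | 52.2% | PR, disagrees |
| down 25% (t = 0.75) | 57.8% | PR, disagrees |

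The switch comes at t = 0.50/0.5625 = 0.889, a fall of about 11% in the third axis. If that axis grows, the conflict can reverse: in-plane factor 0.70 and t = 1.05 give 51.0% by product (PR) and 1 − 0.49 × 1.05 = 48.6% by volume (failure). Disagreement is therefore possible over a realistic range, but it does not always occur.

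**The case against.** **Only part III gives an explicit free choice.** This is correct. Part IV pairs the product with palpable tumour and volume with radiologic assessment, and 8.1a makes volume optional. A reader might infer that the whole of 8.2 treats the measures as interchangeable, and the text does not go that far. The conflict remains even so. Sections 6.3 and 8.1 allow a CT mass to be recorded either way, part V names no measure, and on the strict pairing in part IV a palpable node and a CT mass that shrink equally can still be classed differently.

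**There are partial safeguards.** Lesion size must be recorded before treatment (6.7), CRu is judged against the original measurement, and the Study Chairman settles differences of opinion on response (11.3). A percentage change needs the same units at both times, so a lesion recorded one way at baseline is hard to switch later. This limits drift within a lesion. It does not put different lesions, patients or arms on one scale, and none of these sections says which measure governs.

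**The endpoint is secondary and differences are not expected.** Section 10.4a anticipates about 80% CR and over 90% CR+PR in both arms. This limits the consequences but does not make the definition consistent.

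**Volume is the ideal in 6.3, so it could be the single measure.** That would also remove the ambiguity for CT masses. The product is the more practical choice for scoring: 8.1b already reports it, and palpable nodes are recorded on that scale.

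Four stronger readings are tempting but not supported:

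- **A shift of a stated number of points in the response rates.** The documents do not say how many patients would fall in the windows or how many masses would be scored by volume.
- **Biased failure-free survival.** The documents never define FFS or say that removal under 9.1 counts as an event, so the link is an inference.
- **A compromised primary endpoint.** Molecular response is read from PCR. Removal after four 28-day courses precedes the 12-month assessment, and the handling of removed patients is not stated, so an indirect effect can be neither shown nor excluded.
- **Bias between arms, or uninterpretable rates.** Open treatment makes differential scoring possible, but nothing shows that it occurs. Equal misclassification in both arms would blur the rates without making them meaningless.

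**Conclusion.** The point holds for the secondary clinical response rates. As written, 8.2 III-V with 6.3 and 8.1 can put one CT mass in two categories. Under proportional shrinkage, the PR/failure conflict covers diameter reductions of 20.6% to 29.3%, and the CRu-range/PR conflict covers 37.0% to 50%. The windows depend on how the third axis behaves, and the measures agree if it does not shrink. A CRu call also requires no palpable disease.

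This is a stated rule that gives inconsistent results, which is more than a missing detail. It should be corrected before CR+CRu and CR+PR are compared between arms or set against molecular response. It is not a reason to doubt the primary comparison.

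**What to change.** In 10.4a, state that for the CR+CRu and CR+PR rates every CT mass in both arms is scored on the product of perpendicular diameters, using the percentages already in 8.2. The measure stays the same for each lesion from baseline through all restagings. Volume, where recorded, is reported descriptively.

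Converting the volume cut-offs to 64.6% and 87.5% is a weaker alternative, because those equivalents hold only for uniform shrinkage. If the third axis is unchanged, a 50% product reduction is also a 50% volume reduction, and the converted limit would call it failure.

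The same categories govern removal (9.1) and the maintenance group (5.7.2), so the sponsor must reconcile 6.3, 8.1, 8.2 III-V, 9.1 and 5.7.2. How those clinical rules should operate is for the sponsor, and no clinical cut-off is proposed here.

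**Cost.** The change needs wording, and two diameters can be read from CTs already required. Response rates may look slightly lower than under volume scoring. Any lesion recorded by volume only would need re-reading. The May 2001 amendment concerns the last 25-30 of 210 planned patients, so this could apply to patients entered before a change; the documents do not say how many lesions were recorded that way.

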## 9.0 CRITERIA FOR REMOVAL FROM THE STUDY

- 9.1 Minor responses or failures to respond after delivering the first 4 courses of treatment in this protocol will be removed from the study.
- 9.2 Patients who relapse after achieving remission will be considered for ABMT or if not eligible will be treated with the salvage protocol of highest priority.

## 10.0 STATISTICAL CONSIDERATIONS

### 10.1 Design:

The study will consist of a randomized controlled trial comparing two schedules of the anti-CD20 antibody rituximab, integrated with an established effective front-line chemotherapy program, FND. The primary endpoint will be the molecular complete response rate 12 months after the start of treatment. Since molecular response requires 2 consecutive negative PCR's (see 8.2, part I), a 12-month negative PCR will be considered truly negative only if a 9 or 15 month (or both) are also negative.

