**PATIENT EVALUATION: (Pretreatment and Interim Testing)**

	PRE STUDY	WEEKLY	EVERY 2 COURSES	EVERY 3 COURSES	EVERY 6 MONTHS	POST-THERAPY
H&P	X		X			q 3-6 mo
PS	X					
CBC	X	X				q 3-6 mo
U/A	X					
CXR	X					q 3-6 mo †
SMA 12, K, Mg*	X		X			q 3-6 mo
B2M	X			X		q 3-6 mo
BX/FNA*	X					
BM BX	X			X		q 6 mo †
LAG, CTs	X			X		q 6 mo †
PB markers, Ig's	X			X***		
PB PCR	X				X**	
BM PCR	X				X**	
ECHO or MUGA	X					

♣ K, Mg, etc as indicated, mainly for pts on ATT (see App. B)  
 \* when accessible; for phenotype, gene rearrangement  
 \*\* PCR for bcl-2 q 6 mo yr 1-3, q 12 mo thereafter. Contingency for PCR monitoring at 9 and/or 15 months for selected patients (see 7.2).  
 \*\*\* PB markers, Ig's: until recovery to normal  
 † Restaging off therapy (see section 7.7): at least q 6 mo until relapse or through year 5; then at least yearly

**MISCELLANEOUS INFORMATION: (Include any other information that you feel is pertinent to the study) (Three lines not to exceed 75 characters per line)**

- PCP prophylaxis: TMP/SMX, 2 DS tabs PO twice weekly (q Sat & Sun). For allergy, see section 5.4.3.2
- If PCP pneumonia occurs, subsequent chemotherapy cycles will be given without dexamethasone.

ESTIMATED ACCRUAL:

It is estimated that accrual will be   2   participants per month.

SITE OF STUDY: (please circle the appropriate answer)

This protocol is performed on an:

       INPATIENT              X   OUTPATIENT                   BOTH basis

LENGTH OF STAY: (What is the length and frequency of hospitalization)

RETURN VISITS: (How often must participants come to MDACC)

HOME CARE: (specify what (if any) treatment may be given at home)

WHERE THE STUDY WILL BE CONDUCTED:

- A)  ONLY AT MDACC      B)  MDACC + COMMUNITY PROGRAMS (CCOP, NETWORK)      C)  INDEPENDENT MULTICENTER ARRANGEMENTS

NAME OF SPONSOR/FUNDING SOURCE:

COMPETING PROTOCOLS: (Protocol number(s))

NONE

NAME OF RESEARCH NURSE/DATA MANAGER RESPONSIBLE FOR PROTOCOL:

SUBMIT PROTOCOL TO CLINICAL RESEARCH CENTER REVIEW COMMITTEE:

YES

NO

IF YOUR PROTOCOL HAS A DIAGNOSTIC STEP REQUIRING INFORMED CONSENT AND REGISTRATION ON THE PROTOCOL (E.G., A BLOOD TEST OR BIOPSY) THAT WILL DETERMINE WHETHER OR NOT THE PATIENT WILL SUBSEQUENTLY RECEIVED OR NOT RECEIVED EXPERIMENTAL THERAPY. PLEASE CHECK THE APPROPRIATE BOX(ES) SO THAT THE APPROPRIATE FIELDS MAY BE ESTABLISHED IN PDMS:

BLOOD TEST: YES	NO	BIOPSY: YES	NO	OTHER: YES	NO

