### 10.2 Accrual Rate:

The average yearly accrual rate during the past 4 years on the current low grade lymphoma stage IV clinical trial has been 33 patients per year. Previous experience at M.D. Anderson Hospital has shown that the PCR positivity rate in these stages is in the neighborhood of 60% when tested with the mbr probe only. If the mcr probe is added, approximately 75% of patients can be expected to have a positive PCR at the time of diagnosis. Accrual of the target 128 evaluable patient (see 10.3 e) will therefore take just over 5 years (estimated 5 years, 2 months). Allowing for some inevaluable cases (9% on protocol 88-050), a total accrual of about 185 patients is planned. [Amendment May 2001: Planned accrual changed to 210 patients, with restriction of eligibility to follicular lymphoma only for the last 25-30 patients, so that adequate numbers are entered to fulfill the goal outlined in 10.3.a below. This amendment results from higher-than-expected numbers of patients with small lymphocytic (including MALT) lymphoma being entered.]

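### The primary-endpoint rule in 10.1 does not count patients who are PCR-negative at 6 and 12 months, although 8.2 part I makes them molecular complete responders

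*Combined protocol and SAP*

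**What the plan says.** Section 10.1 makes the molecular complete response rate 12 months after the start of treatment the primary endpoint and adds a confirmation rule. It gives the reason, "Since molecular response requires 2 consecutive negative PCR's (see 8.2, part I"), and then the rule: "a 12-month negative PCR will be considered truly negative only if a 9 or 15 month (or both) are also negative".

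The definition it cites, 8.2 part I, requires a patient with an initially positive blood PCR who "converts to negative on at least 2 consecutive occasions no less than 2 months apart". A positive marrow PCR during that interval disqualifies. The definition names no particular months.

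The samples come from 7.2. The routine schedule is "PCR in the peripheral blood will be followed every 6 months during the first 3 years, then every 12 months", which puts samples at 6, 12 and 18 months. Extra samples depend on earlier results: "For patients who are positive at the 6 month time point an additional PCR assay at 9 months is requested", and, for those "still positive at 9 months, but who are subsequently negative at 12 months, yet another additional assay at 15 months is requested". The footnotes to the synopsis evaluation table and to Appendix A agree that these samples are not for everyone: "Contingency for PCR monitoring at 9 and/or 15 months for selected patients (see 7.2").

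On patients who cannot be assessed, 10.2 has only a general allowance, "Allowing for some inevaluable cases (9% on protocol 88-050"). It does not mention a 12-month negative that lacks a confirming sample.

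**The concern.** The rule in 10.1 depends on samples that the schedule does not request for one group: patients already negative at 6 months. If they stay negative at 12 months, they have two consecutive negatives 6 months apart, which 8.2 accepts, but no 9- or 15-month result, which 10.1 demands. They are the patients who clear early and stay clear.

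This sentence decides who is a responder in the primary analysis. One analyst working from 10.1 and another working from 8.2 would report different primary results from the same data. The documents do not say which governs, nor whether a 12-month negative without the named confirmation is a non-responder or inevaluable.

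**Working it through.** **Step 1. Score each sample path under both rules.** Take only the samples that 7.2 requests, and assume no positive marrow PCR. Four paths end with a negative at 12 months:

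| Result by month | 8.2 part I | 10.1 as written |
|---|---|---|
| 6 neg, 12 neg | responder | not counted (no 9- or 15-month sample requested) |
| 6 pos, 9 neg, 12 neg | responder | responder |
| 6 pos, 9 pos, 12 neg, 15 neg | responder | responder |
| 6 pos, 9 pos, 12 neg, 15 pos | not a responder | not a responder |

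The two rules disagree only on the first path, and there 10.1 drops every patient.

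**Step 2. Reproduce the plan's sample size.** Section 10.3a gives 64 PCR-positive patients per arm for a 25-point difference with the higher rate at 85% (so 60% vs 85%), two-sided alpha 0.05 and power 0.90. With the arcsine formula, h = 2·asin(√0.85) − 2·asin(√0.60) = 0.574, and n = 2 × [(1.960 + 1.282)/h]² = 63.8, which rounds up to 64. The pooled normal formula gives 65. Exact binomial enumeration of the pooled two-proportion z test at 64 per arm gives power 0.903. The stated figure is sound and is not part of this point.

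**Step 3. Illustrate the weight of the disagreement.** Let f be the share of 8.2 responders already negative at 6 months. The documents do not give f, so these values are assumptions, set equal in the two arms. All powers use the exact enumeration of step 2.

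*Dropped patients scored as non-responders.* The counted rate is p(1 − f), with n = 64 per arm. At f = 25%: 0.60 × 0.75 = 45.0% and 0.85 × 0.75 = 63.75%.

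*Dropped patients excluded without replacement.* The rate is p(1 − f)/(1 − pf), with n = 64(1 − pf). At f = 25%:
- Arm 1: 0.45/0.85 = 52.9%, n = 64 × 0.85 = 54.4, taken as 54.
- Arm 2: 0.6375/0.7875 = 81.0%, n = 64 × 0.7875 = 50.4, taken as 50.

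| f in both arms | Power, non-responder | Power, excluded |
|---|---|---|
| 0% | 0.90 | 0.90 |
| 10% | 0.78 | 0.90 |
| 25% | 0.56 | 0.88 |
| 50% | 0.32 | 0.82 |

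Exclusion costs little power but is not neutral, because it removes only responders. At f = 25% it removes 64 × 0.60 × 0.25 = 9.6 patients in arm 1 and 64 × 0.85 × 0.25 = 13.6 in arm 2, or 15% and 21% of 64. The 9% inevaluable figure in 10.2 does not name such patients.

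**The case against.** The best defence is that the intent can be recovered. The sentence in 10.1 opens by pointing to 8.2, which a 6- plus 12-month pair satisfies. The flow-chart footnotes call the 9- and 15-month samples a contingency for selected patients. On that reading, 10.1 was written for patients in the contingency path and overlooked the rest. I think that is very probably what happened. It shows what the correction should say, but it does not remove the need for one: the words in 10.1 are exclusive, they define the primary endpoint, and no other section lets the 6-month sample confirm the 12-month one.

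A second objection also stands in part. Section 7.2 requests extra samples for some patients without forbidding them for others, so a 6-month-negative patient who happens to have a negative 9- or 15-month PCR would qualify. The conflict therefore concerns patients sampled as requested, not every early clearer without exception.

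A reader might infer from 10.3b, which asks whether concurrent rituximab raises the 6-month molecular response rate, that the rule must remove proportionately more arm 2 responders and could erase or reverse the treatment difference. The documents do not support that. Section 10.3b is a hypothesis about 6-month response rates; it says nothing about the share of 12-month responders who clear early in each arm. The arithmetic can produce such a result: f of 25% in arm 1 and 50% in arm 2, with non-responder scoring, gives 45% vs 42.5%. That needs literal application against the evident intent, one particular scoring rule and an unequal f that no section supplies. With the same unequal f and exclusion, the rates are 52.9% vs 73.9%, so the direction holds.

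**Conclusion.** The point holds as a conflict inside the primary-endpoint definition. Sampled as 7.2 asks, a patient negative at 6 and 12 months is a molecular complete responder under 8.2 part I (absent a positive marrow PCR in the interval) and is not counted under 10.1. The wording of 10.1 is wrong for these patients, and it must be corrected because it decides the primary result.

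The conclusion rests on reading 7.2, 8.2 and 10.1 together and needs no assumption about rates. The power figures do need assumptions, about f and about scoring, and they illustrate the stakes without predicting a loss. A reader might take them to mean that the trial is underpowered. The documents do not support that: with the 6-month sample accepted, early clearers count again, so on this point the planned 60% vs 85% and the power of about 0.90 at 64 per arm are unchanged.

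**What to change.** Replace the confirmation sentence in 10.1 with:

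> A 12-month negative blood PCR counts as molecular CR if the adjacent blood PCR at 6 months (when no 9-month sample was taken), 9 months or 15 months is also negative, with no positive marrow PCR in the interval, as defined in 8.2 part I. A patient negative at 12 months without such a confirming sample is scored as a non-responder in the primary analysis, with a sensitivity analysis excluding such patients.

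Under the 7.2 schedule this keeps both paths that 10.1 already accepts and adds the 6- plus 12-month pair. The second sentence classifies those left unconfirmed, such as a patient with a missed 6-month sample, or one positive at 6 months whose 9-month sample was missed and for whom 7.2 therefore requests no 15-month sample.

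Do not widen the primary rule to 18-month confirmation. Arm 1 starts six monthly rituximab doses right after the 12-month sample (5.2.3), and 10.3a relies on that delay to compare with FND alone. The existing rule already allows month 15, so a further sensitivity analysis that disregards confirmation after month 12 in both arms is worthwhile; the documents give no basis for the size of that effect.

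The cost is one replacement sentence of protocol text and two sensitivity analyses on data already collected, with no extra samples or patients and no change in sample size. It should be settled before PCR results are compared by arm.
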